7.6.3. Exploratory Efficacy Analysis

The same efficacy analyses used for the secondary efficacy variables will be used for the exploratory efficacy variables.

7.7. Safety Analysis

All safety data collected on or after the date that study drugs were first dispensed up to the date of last dose of study drugs plus 30 days will be summarized by treatment group. Data for the follow-up period will be included in data listings.

7.7.1. Extent of Exposure

Data of a subject's extent of exposure to study drug will be generated from the study drugs administration eCRF data. Exposure data will be summarized by treatment group.

7.7.2. Adverse Events

Clinical and laboratory AEs will be coded using the Medical Dictionary for Regulatory Activities (MedDRA). System Organ Class (SOC), High-Level Group Term (HLGT), High-Level Term (HLT), Preferred Term (PT), and Lower-Level Term (LLT) will be attached to the clinical database. AE severity will be graded using the CTCAE. Events will be summarized on the basis of the date of onset for the event. A TEAE will be defined as one or both of the following:

- Any AEs with an onset date on or after the study drugs start date and no later than 30 days after permanent discontinuation of study drugs
- Any AEs leading to premature discontinuation of study drugs

Summaries (number and percentage of subjects) of TEAEs and SAEs by SOC and PT will be provided by treatment group. Treatment-emergent AEs will also be summarized by relationship to study drugs and severity. In addition, TEAEs leading to premature discontinuation of study drugs and study, and SAEs leading to death will be summarized and listed.

All AEs collected during the course of the study will be presented in data listings with a field for treatment-emergent event (Yes/No).

7.7.3. Laboratory Evaluations

Selected laboratory data will be summarized (n, mean, SD, median, minimum, and maximum) by treatment group and study visit along with the corresponding change from baseline values.

Graded laboratory abnormalities will be defined using the grading scheme in the CTCAE. Grading of laboratory abnormalities for analysis purposes will be defined in the Statistical Analysis Plan.

The incidence of treatment-emergent laboratory abnormalities, defined as values that increase at least one toxicity grade from baseline at any time post baseline up to and including the date of last dose of study drugs plus 30 days, will be summarized by treatment group. If baseline data are missing, then any graded abnormality (i.e., at least a Grade 1) will be considered treatment-emergent.

7.8. Pharmacokinetic Analysis

Plasma concentrations of EFX will be listed and summarized pre-dose and between 48-96 hours post-dose at the timepoints listed in the Schedule of Assessments. Noncompartmental parameters will be listed and summarized descriptively.

7.9. Biomarker Analysis

Descriptive statistics of biomarker change from baseline will be provided at each sampling time by treatment. Point estimates and 95% confidence intervals may be calculated.

Exploratory analyses may also be performed to evaluate the association of individual exploratory biomarkers or combination of biomarkers with clinical measurements and other risk factors.

Additional exploratory analyses that could enhance the understanding of the biological effects and the mechanism of action of EFX may be added in the Biomarker Analysis Plan if necessary.

7.10. Sample Size

Main Study:

Due to the exploratory nature of this study, no formal power calculations were used to determine sample size. The number of subjects was chosen based on clinical experience with other similar proof of concept studies.

With the following assumptions, the power for N = 20 subjects with active treatment is approximately 91% to detect:

- a true, baseline-adjusted, mean decrease from baseline in MRI-PDFF-estimated hepatic fat of 5% compared to placebo,
- with a one-sided t-test for decrease from placebo,
- a 5% significance level,
- 20 subjects receiving placebo, and
- a standard deviation estimated as 5.2% (Sanyal et al. 2019).

Cohort C:

Since the primary objective is to assess the safety and tolerability of EFX in NASH subjects with compensated cirrhosis, the sample size is determined based on clinical considerations, and the treatment comparisons of efficacy measurements are not powered.

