1.6. Rationale for Selection of Dose

As described in Section 1.4.1 and Section 1.4.2, in the Phase 1a/1b studies, EFX appeared to be well tolerated at doses up to 70 mg SC. There were no patient deaths and no SAEs attributable to treatment with EFX. The most common AEs were gastrointestinal disorders, such as mild diarrhea and nausea.

Exploratory analyses for Study 20100018 (Section 1.4.2) were conducted by Akero to demonstrate the dose-related change from baseline for lipoproteins and markers of insulin sensitivity, observed following administration of 21 mg and 70 mg QW doses of EFX, compared to placebo. Significant improvements for each marker of insulin sensitivity were observed at the 70 mg QW dose, consistent with agonism of FGFR1c in adipose tissue.

The analysis indicates maximal or near maximal effects were observed by the third dose of 70 mg QW for lipoproteins, and by the fourth dose for markers of insulin sensitivity. Reductions in triglyceride and increases in HDL-C were significant at all time points from Day 4 through Day 57, while non-HDL-C was significantly lower from Day 15 through Day 57. Taken together with published clinical data for third-party FGF21 analogs, the

time-course and magnitude of changes in lipoproteins observed at the 70 mg QW dose suggest that EFX has the potential to rapidly and durably reduce liver fat in patients with NASH. Notably, EFX's effects appear to be sustained for three weeks after the final dose, including significant increases of 39% in HDL-C and significant reductions of 28% and 67% in non-HDL-C and triglycerides, respectively, observed on Day 43.

At 21 mg QW, there were also indications of improved sensitivity to insulin, with a significantly lower level of C-peptide observed after the fourth dose, and a trend toward lower levels of insulin and a lower calculated value of HOMA IR. Although liver fat was not measured in Study 20100018, the magnitude and robustness of effects on lipoproteins at 21 mg and 70 mg QW will likely translate into substantial reductions in liver fat with longer term treatment.

Efficacy for the proposed Phase 2a study is predicted based on PK/PD modeling. The doses to be tested are expected to mediate potentially beneficial changes in PD parameters including triglycerides and LDL. PK/PD modeling suggests that the dose range selected will achieve approximately 45% to 90% of the maximum effect on triglycerides and LDL.

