7.6. Efficacy Analysis

7.6.1. Primary Efficacy Analysis

The primary efficacy variable will be the absolute change from baseline hepatic fat fraction measured by MRI-PDFF at Week 12. Summary statistics (number of subjects, mean, standard deviation, median, minimum, and maximum) at all visits and change from baseline will be provided. The primary efficacy analysis will be analyzed with an analysis of covariance (ANCOVA) model with treatment group and F1 fibrosis score as factors and baseline hepatic fat fraction measured by MRI-PDFF as a covariate. For any subjects in the full analysis set (FAS) with a missing primary efficacy value, the primary efficacy variable will be imputed with multiple imputation method. The specification of the multiple imputation method will be provided in the SAP. The treatment effect of each active dose comparing with placebo will be estimated from the ANCOVA model. LS means, one-sided, 97.5% confidence intervals and one-sided p-values will be calculated. In order to control the Type I error rate inflation caused by multiplicity issues, a step-down fixed hypothesis testing sequence will be used. That is, only high dose is proved to be significantly better than placebo will the next low dose be compared.

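### The 91% power is correct for one stand-alone comparison but names no dose; under the step-down sequence it applies only to 70 mg, and an equal 5-point effect at every dose gives about 85% for 50 mg and 80% for 28 mg

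*Protocol*

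**What the plan says.** Protocol section 7.10 states for the Main Study that "the power for N = 20 subjects with active treatment is approximately 91% to detect" the assumed benefit, which it gives elsewhere in the list as a "mean decrease from baseline in MRI-PDFF-estimated hepatic fat of 5% compared to placebo", after adjustment for baseline. The other listed conditions are an SD of 5.2 percentage points, a placebo arm of 20, and a t-test, one-sided in the direction of a decrease, at "a 5% significance level". The synopsis repeats the statement and adds that the 5% is absolute. Neither place says which of the three active doses the figure describes, and neither mentions the testing sequence.

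Section 7.10 opens by calling the study exploratory and saying that no formal power calculation determined the sample size.

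Section 7.6.1 prescribes a fixed step-down sequence to control the type I error rate: "only high dose is proved to be significantly better than placebo will the next low dose be compared". With doses of 70, 50 and 28 mg, that order is 70, then 50, then 28. The same section estimates every dose against placebo from one ANCOVA and reports one-sided 97.5% confidence intervals and one-sided p-values.

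The SAP supplied covers Cohort C only. Its introduction says that the Main Study has a separate SAP.

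**The concern.** A power figure with no dose attached invites the reader to apply it to each active arm. Under a fixed sequence that is right only for the first test. A lower dose can be declared effective only if its own test and every test above it succeed, so its power is a joint probability. Unless success at the higher doses is practically certain, that joint probability is below the stand-alone figure.

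At stake is how the lower doses are read. The study compares three doses, and someone who believes that each had 91% power will give too much weight to a 50 mg or 28 mg result that is non-significant or was never formally tested.

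**Working it through.** **Inputs.** Section 7.10: difference 5 points, SD 5.2 points, 20 active and 20 placebo subjects, one-sided t-test at 5%. Section 5.2.2: 20 subjects in each of the four arms, hence one placebo arm for all three comparisons. Section 7.6.1: order 70, 50, 28 mg, each step requiring success at the step before.

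**Step 1: reproduce the stated figure.**
- Standard error of a difference: 5.2 × √(2/20) = 1.644.
- Noncentrality: 5 / 1.644 = 3.04.
- Degrees of freedom: 20 + 20 − 2 = 38; one-sided 5% critical value 1.686.
- Power = P(noncentral t with 38 df and noncentrality 3.04 exceeds 1.686) = 0.910.

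The 91% is therefore reproduced as the power of one comparison standing alone.

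**Step 2: write down the sequence.** Let R70, R50 and R28 be the events that each dose's own test is significant.
- Power for 70 mg = P(R70).
- Power for 50 mg = P(R70 and R50).
- Power for 28 mg = P(R70 and R50 and R28).

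Equal arms sharing one placebo group give a correlation of 0.5 between any two dose-placebo differences, so the tests cannot be treated as independent. Independence would give 0.91² = 0.83 and 0.91³ = 0.75, which is too low.

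**Step 3: evaluate with a true effect of 5 points at every dose.** Simulation of four arms of 20 with a shared placebo arm, one-sided 5%, 1,000,000 replicates:

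| Test used | 70 mg | 50 mg | 28 mg |
|---|---|---|---|
| Pairwise t, 38 df | 91.0% | 84.8% | 80.1% |
| Pooled variance, 74 df (closer to the ANCOVA) | 91.4% | 85.5% | 81.0% |
| Normal approximation | 91.9% | 86.1% | 81.7% |

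The shortfall against 91% is about 6 points for 50 mg and 11 points for 28 mg on the pairwise t. The choice of test moves the results by less than 2 points.

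**Step 4: let the higher doses have larger effects.** Pairwise t, one-sided 5%, 400,000 replicates, effects in the order 70/50/28 mg (assumed values):
- 6/5/4: the 50 mg dose, with a 5-point effect, reaches 89%.
- 7/6/5: the 28 mg dose, with a 5-point effect, reaches 89%.

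In these cases the sequence costs a 5-point dose about 2 points (91% − 89%).

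**Step 5: the significance level.** A one-sided 97.5% interval corresponds to a one-sided 2.5% test, not 5%. At 2.5% the critical value on 38 df is 2.024. With 5 points at every dose the pairwise t gives 84.2% for 70 mg, 74.7% for 50 mg and 67.9% for 28 mg.

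**The case against.** The strongest reply is that nothing in section 7.10 is miscalculated. It sets out one comparison, lists its conditions and gives the right answer; quoting per-comparison power in a multi-dose proof-of-concept study is common. The section also says that the sample size did not come from a formal power calculation, so no design decision rests on the figure. Section 7.6.1 provides an estimate for every dose, which gives some protection to a dose that is never formally tested. The Main Study SAP, which is not available here, may settle the testing level and the power of the later steps.

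Most of this stands. The point concerns labelling, it does not call for more subjects, and its weight is limited. What survives is that the protocol gives a power figure in two places beside a rule that confines that figure to one of three doses, and says so in neither.

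Two stronger readings are tempting and are not supported.

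*That 85% and 80% are ceilings for a 5-point effect.* They follow from 5 points at every dose. Step 4 of the working shows that a lower dose with a 5-point effect comes close to 91% when the doses above it do better.

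*That the lower doses had little chance of success.* Section 1.6 says that "the dose range selected will achieve approximately 45% to 90% of the maximum effect on triglycerides and LDL", and a reader might carry that two-fold spread over to liver fat, for example as effects of 5, 4 and 2.5 points. The step-down powers would then be 91%, 73% and 39%. But stand-alone power with no sequence at all is already 77% for 4 points and 44% for 2.5 points, so the sequence accounts for only 4 to 5 points of the loss; the rest comes from assuming smaller effects. The modelling concerns triglycerides and LDL, not liver fat, and gives no value for 50 mg. The weekly-dosing triglyceride results in section 1.4.2.3 suggest a flatter curve: falls of up to 55% at 21 mg and 69% at 70 mg, a ratio of 55/69, or about 80%.

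**Conclusion.** The concern holds as a matter of an unqualified statement, not of wrong arithmetic. The 91% is per-comparison power, and under section 7.6.1 it is the power for 70 mg only. The figures of about 85% for 50 mg and 80% for 28 mg rest on a true effect of 5 points at all three doses, SD 5.2, 20 analysed subjects per arm, a shared placebo arm and a one-sided 5% level. With larger effects at the higher doses the shortfall shrinks and can nearly vanish.

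The level is itself uncertain. If testing follows the 97.5% intervals, even the first step falls short of 91%, at about 84%, and the later steps are about 75% and 68%. The documents supplied do not settle which level governs.

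**What to change.** 1. Reconcile the 5% level in section 7.10 with the one-sided 97.5% intervals in section 7.6.1, checking against the Main Study SAP, and state one testing level in both places. This comes first because every power figure depends on it.
2. In section 7.10 and the synopsis, say that 91% is per-comparison power and that under the testing sequence it applies to the first step, 70 mg against placebo.
3. Add the step-down powers, about 85% for 50 mg and 80% for 28 mg, labelled as assuming an equal 5-point effect at all doses. If the level is settled at one-sided 2.5%, use about 84%, 75% and 68% for the three steps instead.

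Do not add a declining dose-response scenario based on the triglyceride and LDL modelling.

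Once the level is settled, the cost is about two sentences in each place and a less favourable figure for the lower doses. Sample size, analysis model and testing order stay as they are.

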7.11. Data Monitoring Committee

An external DMC that consists of two hepatologists, one cardiologist and a statistician will review the progress of the study. The DMC will convene after 20 subjects (approximately 5 per treatment group) have completed the Week 4 assessments in the Main Study. The DMC will convene again after 10 subjects have completed the Week 4 assessments in Cohort C. The DMC will receive all reports of SAEs including potential DILI and liver decompensation events and convene as needed to monitor for safety. The DMC will provide recommendations to Akero whether the nature, frequency, and severity of adverse effects associated with study treatment warrant the early termination of the study in the best interests of the participants, whether the study should continue as planned, or the study should continue with modifications. The DMC may also provide recommendations as needed regarding study design. The DMC's specific activities will be defined by a mutually agreed charter, which will define the DMC's membership, conduct, and meeting schedule.

While the DMC will be asked to advise Akero regarding future conduct of the study, including possible early study termination, Akero retains final decision-making authority on all aspects of the study.

7.11.1. Stopping Rules

The DMC will be convened based on emerging safety data if any of the following occur:

- One or more subjects develop the same treatment-emergent grade 5 adverse event or lab abnormality (confirmed by repeat testing) deemed related to EFX.
- Two or more subjects develop the same treatment-emergent grade 4 or higher adverse event or lab abnormality (confirmed by repeat testing) deemed related to the same dose level of EFX.
- Three or more subjects develop the same treatment-emergent grade 3 or higher adverse event or lab abnormality (confirmed by repeat testing) deemed related to the same dose level of EFX.

The DMC will assess the causality and clinical relevance of the adverse events or lab abnormalities and recommend to either halt study dosing for all subjects, pause enrollment, or take no action. If enrollment or dosing is paused, it may be resumed (with or without modifications) only after further review of all available safety data and agreement by the appropriate regulatory agencies.

7.12. Adjudication Committee

An external adjudication committee may be established to adjudicate cases that meet protocol-defined criteria for hepatic decompensation events and possible cases of druginduced liver injury following DMC review and escalation.

8. ADMINISTRATIVE CONSIDERATIONS

8.1. Investigator Responsibilities

8.1.1. Good Clinical Practice

The Investigator will ensure that this study is conducted in accordance with the principles of the Declaration of Helsinki, International Council for Harmonisation (ICH) guidelines, or with the laws and regulations of the country in which the research is conducted, whichever affords the greater protection to the study subject. These standards are consistent with the European Union Clinical Trials Directive 2001/20/EC and Good Clinical Practice Directive 2005/28/EC.

The Investigator will ensure adherence to the basic principles of Good Clinical Practice, as outlined in 21 Code of Federal Regulations (CFR) 312, subpart D, "Responsibilities of Sponsors and Investigators," 21 CFR, part 50, 1998, and 21 CFR, part 56, 1998.

The Investigator and all applicable subinvestigators will comply with 21 CFR, Part 54, 1998, providing documentation of their financial interest or arrangements with Akero, or proprietary interests in the investigational drug under study. This documentation must be provided prior to the Investigator's (and any subinvestigator's) participation in the study. The Investigator and subinvestigator agree to notify Akero of any change in reportable interests during the study and for 1 year following completion of the study. Study completion is defined as the date when the last subject completes the protocol-defined activities.

8.1.2. Institutional Review Board (IRB)/Independent Ethics Committee (IEC)/ Ethics Committee (EC) Review and Approval

Before initiating a trial, the Investigator (or Sponsor as appropriate according to local regulations) will submit this protocol, ICF, and any accompanying material to be provided to the subject (such as advertisements, subject information sheets, or descriptions of the study used to obtain informed consent) to an IRB/IEC/EC. The Investigator will not begin any study subject activities until approval from the IRB/IEC/EC has been documented and provided as a letter to the Investigator.

Before implementation, the investigator will submit to and receive documented approval from the IRB/IEC/EC any modifications made to the protocol or any accompanying material to be provided to the subject after initial IRB/IEC/EC approval, with the exception of those necessary to reduce immediate risk to study subjects.

8.1.3. Informed Consent

Eligible subjects may only be included in the study after providing (witnessed, where required by law or regulation), IRB/IEC-approved informed consent, or, if applicable after such consent has been provided by a legally acceptable representative(s) of the subject. Informed consent must be obtained before conducting any study-specific procedures (e.g., all

of the procedures described in the protocol). The process of obtaining informed consent must be documented in the subject source documents.

The investigator must use the most current IRB/IEC/EC-approved consent form for documenting written informed consent.

8.1.4. Confidentiality

The investigator will ensure that subjects' anonymity will be strictly maintained and that their identities are protected from unauthorized parties. Only partial date of birth (as applicable in certain countries), another unique identifier (as allowed by local law), and an identification code will be recorded on any form or biological sample submitted to the Sponsor, IRB/IEC/EC, or laboratory. Laboratory specimens must be labeled in such a way as to protect subject identity while allowing the results to be recorded to the proper subject. Refer to specific laboratory instructions. The investigator will keep a screening log showing codes, names, and addresses for all subjects screened and for all subjects enrolled in the trial. Subject data will be processed in accordance with all applicable regulations.

The investigator agrees that all information received from Akero, including but not limited to the IB, this protocol, eCRFs, the IMP, and any other study information, remain the sole and exclusive property of Akero during the conduct of the study and thereafter. This information is not to be disclosed to any third party (except employees or agents directly involved in the conduct of the study or as required by law) without prior written consent from Akero. The investigator further agrees to take all reasonable precautions to prevent the disclosure by any employee or agent of the study site to any third party or otherwise into the public domain.

8.1.5. Study Files and Retention of Records

The investigator must maintain adequate and accurate records to enable the conduct of the study to be fully documented and the study data to be subsequently verified. These documents should be classified into at least the following two categories: (1) Investigator's study file, and (2) subject clinical source documents.

The investigator's study file will contain the protocol/amendments, CRF and query forms, IRB/IEC/EC and governmental approval with correspondence, informed consent, drug records, staff curriculum vitae and authorization forms, and other appropriate documents and correspondence.

The Investigator must maintain source documents for each subject in the study, consisting of case and visit notes (hospital or clinic medical records) containing demographic and medical information, laboratory data, electrocardiograms, and the results of any other tests or assessments. All information on CRFs must be traceable to these source documents in the subject's file. Data not requiring a separate written record will be defined before study start and will be recorded directly on the CRFs. The Investigator must also keep the original informed consent form signed by the subject (a signed copy is given to the subject).

The Investigator must give the monitor access to all relevant source documents to confirm their consistency with the data capture and/or data entry. Akero monitoring standards require full verification for the presence of informed consent, adherence to the inclusion/exclusion criteria, documentation of SAEs, and of data that will be used for all primary variables. Additional checks of the consistency of the source data with the CRFs are performed according to the study-specific monitoring plan. No information in source documents about the identity of the subjects will be disclosed.

All clinical study documents must be retained by the investigator until at least 2 years or according to local laws, whichever is longer, after the last approval of a marketing application in an ICH region (i.e., United States, Europe, or Japan) and until there are no pending or planned marketing applications in an ICH region; or, if no application is filed or if the application is not approved for such indication, until 2 years after the investigation is discontinued and regulatory authorities have been notified. Investigators may be required to retain documents longer if specified by regulatory requirements, by local regulations, or by an agreement with Akero. The investigator must notify Akero before destroying any clinical study records.

Should the investigator wish to assign the study records to another party or move them to another location, Akero must be notified in advance.

If the investigator cannot provide for this archiving requirement at the study site for any or all of the documents, special arrangements must be made between the investigator and Akero to store these records securely away from the site so that they can be returned sealed to the investigator in case of an inspection. When source documents are required for the continued care of the subject, appropriate copies should be made for storage away from the site.

